We will enroll equal numbers of male and female MetS adults ($n = 30$; 18-50 y) from the Columbus, OH area as we detailed¹ to complete a 2-arm, randomized controlled, cross-over trial. Participants will be randomized in 3-unit blocks to receive a *DGA*-based diet containing Russet Burbank potatoes (350 g/d; 260 kcal; 12.4 g resistant starch) or an energy-matched bagel that is nearly devoid of resistant starch. Our approach closely follows recommendations of the *DGA*² and entails high scientific rigor by providing all foods during each 14-d intervention. On day 0, 7, and 14 of each period, coinciding with when participants obtain prescribed foods, we will assess anthropometrics (weight, height, waist circumference) and blood pressure. At baseline (day 0) of each trial, fasting glucose, insulin, and endotoxin will be measured to verify stable health status. Following each 14-d intervention, participants will provide a fecal sample and undergo testing in the fasted state for metabolic endpoints, gut barrier function, and VEF. Then, they will receive a glucose challenge (75 g) to examine VEF in relation to PPH at 30 min intervals for 2 h. Gut permeability probes (sucralose, erythritol, lactulose, mannitol) will also be co-administered on day 14, and urine collected for 24-h. After completing a 2-wk washout period (i.e. to restore microbiota composition³), participants will receive the alternate treatment (i.e. *DGA* diet + potato or bagel) and repeat all procedures.

B. Study Subjects

Enrollment Criteria. MetS adults will be studied because of their impaired VEF in association with glucose intolerance.⁴ We will enroll those who are unmanaged (i.e. no drug therapy) and they will be required to meet these established MetS criteria⁵ to improve homogeneity of study outcomes: i) fasting glucose 100-126 mg/dL, ii) waist circumference >102 cm for men or >88 cm for women, and iii) fasting triglyceride >150 mg/dL. We anticipate that they may also fulfill other MetS criteria, specifically HDL-C (<40 mg/dL for men, <50 mg/dL for women) and elevated blood pressure⁶ (>120/80 mmHg); these will be considered for co-variate analysis. Other inclusion criteria are: i) non-smoker, ii) non-dietary supplement user (>1-mo), iii) free of gastrointestinal disorders, CVD,

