cancer, and iv) no recent use of antibiotics, or any medications affecting glycemia, lipidemia, or blood pressure. Participants having any of these ***exclusion criteria*** will not be enrolled: i) use of anti-inflammatory agents or probiotics, ii) vegetarian, gluten intolerant, carbohydrate-restricted diet, iii) alcohol intake >2 drinks/d, or iv) ≥ 7 h/wk of aerobic activity.

Power Calculation. Plasma glucose and FMD during the 2-h postprandial period ($AUC_{0-120\text{ min}}$) and fasting endotoxin following 14-d controlled feeding have been selected as the **primary outcome variables**. These endpoints had no gender differences ($P>0.05$) in our prior studies. PPH was also inversely related ($P<0.001$) to FMD.^{4,7} MetS adults had improved FMD following low-fat milk ingestion compared with rice milk ($AUC_{0-3\text{ h}}: 1150\pm145$ vs 908 ± 118 , CV=56%) and attenuated PPH.⁴ For this study, we predict that FMD_{AUC} will be 25% greater in DGA+Potato during the oral glucose challenge on day 14. Thus, 26 MetS subjects would be needed to detect a treatment effect with >80% power ($P<0.05$). We will therefore enroll 30 subjects to account for unexpected attrition and increase power. A similar power calculation was performed using endotoxin measured from MetS vs. healthy adults.¹ To detect a 25% predicted lowering of endotoxin, 22 MetS subjects would be needed. Based on our preliminary data, DGA+Potato could lower endotoxin by increasing vitamin C status in addition to alleviating gut dysbiosis in a resistant starch-dependent manner. This secondary hypothesis will be tested by measuring vitamin C on day 14 using our routine HPLC-ECD method.¹

Statistical Analysis Plan

Most data in will be analyzed by linear mixed effects models (LMMs) with random effect for subjects (to account for repeated measures) and fixed effects for gender, time period, and their interactions. Multivariate regression analysis will define pairwise correlations between study variables in the presence or absence of potential study covariates. Statistical significance for all analyses will be set at $P<0.05$.

C. Detailed Study Procedures

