Overview of Study Procedures. Potential participants who call the study center in an anonymous manner for more information as well as those identified through ResearchMatch will be given a brief description about the study and asked a few questions to determine their eligibility (see *Phone Script* attachment). If they meet the eligible criteria, they will be invited to the study center for a screening meeting. During the meeting, the Informed Consent (see *Informed Consent* attachment) will be explained and provided for them to review. The participant will then be given the opportunity to review the Informed Consent form. If he/she chooses to participate in the study, they will then be asked to provide written consent. Women choosing to participate will also be asked to complete the *Menstrual History Questionnaire*. After receiving informed consent, the participants' height, weight, waist circumference, and blood pressure will be measured. Additionally, a small fasting blood sample will be collected for blood chemistry analysis. If they are not fasted at least 10 hours, they will be asked to come back in the fasted state at time of mutual convenience. These blood results in combination with anthropometric parameters will determine the participant's eligibility. Eligible participants who agree to proceed with the study will then complete two 2-week intervention periods in a randomized order, each followed by a 2-h postprandial trial. We estimate that completion of all study procedures will take ~6-12 weeks per participant. Each step of the study procedure will be discussed in detail below:

Screening Meeting. Potential participants who have met the initial criteria of the study (based on the telephone interview) will be invited to the study center at a mutually convenient time. During this time, the participant and a member of the research team will meet in a private, quiet conference room or office. The individual will be provided the informed consent form, and its contents will be

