Potential participants who meet the criteria will be contacted within a few days after their screening meeting to provide them with their blood and body measurement results and inform them of their eligibility to participate in the study. Consistent with our CLIA exemption, blood results will be provided in a categorical manner (i.e. "normal", "marginally high", "high") rather than providing actual blood concentrations of lab values (see *Subjects Results Sheet*). Potential participants having any blood values outside of the "normal range" will be directed/encouraged to follow-up with their own physician. Those having body measurements, blood pressure, and blood values within acceptable limits (see Inclusion/Exclusion criteria), will be invited to participate in the study. Subjects will be included or excluded based on a best fit of the inclusion and exclusion criteria (an example of best fit would be if a potential subject says he/she exercises 8 h/wk, which is close to our exclusion criteria of 7 h/wk, they might still be included in the study if they meet all other inclusion and exclusion criteria more closely than other potential subjects). Participants will be read one phone script if they qualify and another phone script if they do not qualify (see *Participant Eligibility Phone Script* attachment). Potential participants who qualify for the study will be communicated a message as follows: "Congratulations! You have been selected for participation in our study based on your blood testing results. A study investigator will be telephoning you to invite you to the testing session. Would you like to know your blood chemistry results?" Subjects not selected for study will be told the following message: "You have not been chosen for our study, but thank you for your interest." This message will be followed by an explanation why they were not chosen, such as lab values outside of the range we are looking for: "Your blood testing data is.....we were looking for participants who had levels less than". "We can provide you a copy of your results if you would like.....how would you like us to provide them to you?". "You should also consider sharing these results with your physician."

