Test trials. At the end of the intervention period (day 14), participants will report back to the laboratory in the fasted state (10-12 hours) for assessment of height, weight, waist circumference, blood pressure, serum glucose, serum insulin, and serum endotoxin. Participants will return a stool sample collected on day 13 of the intervention period at home. Participants will ingest a sugar solution containing 75 g glucose, which we and others have routinely shown to induce PPH, oxidative stress, and VED. This will be co-ingested with 1 g sucralose, 1 g erythritol, 1 g mannitol, 5 g lactulose for assessment of gut permeability. Then, at 30 min intervals during the 2 h postprandial period, we will assess blood markers and brachial artery flow-mediated dilation. During each study visit, participants will have access to drinking water and use of the restroom as needed. Urine will be collected during the 2 h postprandial period in the laboratory, and participants will be instructed on urine collection for when they return home following their laboratory visit. Participants will return to the study center the following day to drop off their 24-h urine collection containers. To ensure that the order by which each participant completes each trial is randomized, a random sequence generator (<http://www.random.org/sequences/>) will be used to determine the order by which each participant will undergo the two trials.

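### Blocks of three cannot divide two diet sequences equally, so 15:15 is not assured; the loss is small, and an even block size is a cheap improvement

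*Combined protocol and SAP*

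**What the plan says.** - **Allocation.** Section II.A (Study Design) states "Participants will be randomized in 3-unit blocks to receive a" DGA-based diet with potatoes or an energy-matched bagel, followed by the other diet after washout. The Overview of Study Procedures (II.C) says that eligible participants "will then complete two 2-week intervention periods in a randomized order". No ratio, block composition, stratification by sex or rule pairing 2:1 with 1:2 blocks is given.
- **Generation of the order.** Test trials (II.C) says that an online random sequence generator "will be used to determine the order by which each participant will undergo the two trials". It mentions no blocks.
- **Size.** The Power Calculation arrives at 26 subjects for more than 80% power and adds: "We will therefore enroll 30 subjects to account for unexpected attrition and increase power".
- **Model.** The Statistical Analysis Plan describes linear mixed models with a random subject effect and "fixed effects for gender, time period, and their interactions". Neither diet nor sequence is named in that list.
- **Meaning of period.** Study Design uses the word for the feeding periods ("On day 0, 7, and 14 of each period"). The Power Calculation also uses it for the two hours after the glucose drink ("Plasma glucose and FMD during the 2-h postprandial period").
- **Selection.** The Screening Meeting text says "Subjects will be included or excluded based on a best fit of the inclusion and exclusion criteria", so staff have some discretion over who enters.

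**The concern.** An ordinary purpose of blocking in a two-sequence crossover is to keep the numbers per sequence equal. With a block size of three this is impossible within any completed block: the best available split is 2:1 or 1:2. Equality over ten blocks can then arise only by chance.

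Unequal sequences do not unbalance the diets, because everyone receives both. They make diet and study period partly confounded. If the model contains study period, the price is a slightly larger variance. If it does not, part of any difference between first and second period is carried into the diet comparison. The time-period term could mean study period or time after the glucose drink, so the plan leaves open which of these applies. Two sections also describe how the order is generated, and only one mentions blocks.

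**Working it through.** **Inputs.** Block size 3 and N = 30 (II.A), hence 10 blocks; 26 subjects for more than 80% power and significance at P<0.05 (Power Calculation). Assumptions: each block is 2:1 or 1:2 with equal chance; tests are two-sided; 26 subjects give exactly 80%.

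**The plan's own figure.** The plan gives no sequence split to reproduce. The 26 cannot be rebuilt because the within-subject correlation is not stated. Taking the printed CV of 56% as the SD of the paired difference, a 25% effect needs 42 subjects (noncentral t); a correlation of about 0.70 returns 26. The 26 is not disputed here and serves only to scale the power loss.

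**Step 1: sequence split.** The number in one sequence is n1 = 10 + Binomial(10, 0.5).
- 15:15: 252/1024 = 24.6%
- gap of 4 or more: 352/1024 = 34.4%
- 18:12 or worse: 112/1024 = 10.9%
- 20:10: 2/1024 = 0.2%

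**Step 2: precision with study period in the model.** The variance relative to 15:15 is (1/n1 + 1/n2)/(2/15), and the effective N is 30 divided by that ratio. The standardised paired difference giving 80% at N = 26 (24 df) is 0.573. Power at 30 enrolled uses 28 df.

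| Split | Variance ratio | Effective N | Power |
|---|---|---|---|
| 15:15 | 1.000 | 30.0 | 85.7% |
| Mean over lists | 1.0115 | 29.66 | 85.3% |
| 18:12 | 1.042 | 28.8 | 84.3% |
| 20:10 | 1.125 | 26.7 | 81.5% |

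**Step 3: without study period in the model.** Let π be the second-minus-first period effect. The expected potato-minus-bagel difference is the diet effect minus π in the potato-first sequence and plus π in the other. The overall mean therefore carries π(n2 − n1)/30. The share is 6/30 = 20% at 18:12. Its root-mean-square over lists is √10/30 = 10.5%, and its average is zero. The documents give no size for π.

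**Step 4: alternatives at N = 30, one overall list.**
- Simple randomisation: gap of 4 or more in 58% of lists, so blocks of three are still better than no blocks.
- Fixed blocks of 6: always 15:15.
- Fixed blocks of 4: 15:15 in 67%, otherwise 16:14.
- Blocks of 4 and 6 in random order: 15:15 in 77%, otherwise 16:14.

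**Step 5: separate lists by sex, 15 each.**
- Blocks of 6: 15:15 overall in 164/400 = 41%, and 18:12 is possible.
- Blocks of 4: three full blocks plus three places from a 2:2 block, so 8:7 or 7:8 per sex and at worst 16:14 overall. Allocations determined: (3 × 1.333 + 0.333)/15 = 29%.
- Blocks of 2: the same splits, but 7/15 = 47% determined.

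**Step 6: dropout.** If 4 of 30 leave at random (an assumption), 26 completers are 13:13 in 40% of cases with blocks of 6 and 24% with blocks of 3. The mean variance ratios are 1.005 and 1.017.

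**Step 7: predictability.** For someone who knows the block size and past allocations, the share fully determined is 1.5/6 = 25% with fixed blocks of 6, 1.33/4 = 33% with blocks of 4, and (1/3)/3 = 11% with the assumed blocks of 3.

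**The case against.** The strongest reply is that this hardly matters. The average loss is 0.4 power points, and even the most extreme list keeps 81.5%. The SAP lists a time-period effect, and study period is a natural reading of it. Even blocks also have a price: determined allocations rise from 11% to 25% or 33%, while staff can see which food they hand out, have discretion over enrolment, and work under a plan that describes no concealment of the list. All of this stands. It limits the point to a low-severity improvement and shapes the fix.

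Several stronger readings are tempting but unsupported:
- **That the diet comparison is unbalanced.** Each participant receives both diets.
- **That 15:15 is impossible.** Five blocks tilted each way give it.
- **That the result is biased.** This needs a model without study period, a real period effect and an unequal list. The documents establish none of the three.
- **That power falls below target.** On the calibration above, no possible list of 30 completers does this.
- **That the two randomisation passages contradict each other.** The generator could have been used to build the blocked list. If it means unblocked allocation, the block-of-three figures do not apply and imbalance is more likely.

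**Conclusion.** The point holds as a minor design weakness. Blocks of three do not secure equal sequence numbers, and nothing else in the plan does. Under the equal-chance assumption, three lists in four are unequal, but most of these are only mildly so. With study period in the model the mean variance penalty is 1.1%. Without it, a fraction |n1−n2|/30 of an unknown period effect enters the estimate in the list drawn. No shift in the trial's result is claimed. The percentages depend on the assumed block composition, and the power figures on 26 subjects giving exactly 80% and on a diet term being in the model. That a block of three cannot be split equally depends on no assumption.

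**What to change.** 1. **Study Design (II.A).** State that participants are randomised 1:1 to the two diet sequences in permuted blocks of even size from one overall list. Blocks of 4 and 6 in random order are at worst 16:14; fixed blocks of 6 give 15:15 at full enrolment.
2. **Test trials (II.C).** Say that the random sequence generator produces that list, so that both sections describe one procedure.
3. **Statistical Analysis Plan.** Name the fixed effects as diet, study period (first or second), gender and, for repeated postprandial measures, time after the glucose drink. This also guards against imbalance from chance or dropout.
4. **If lists by sex are wanted,** use blocks of 4 within sex, not 6 (18:12 possible) or 2 (same balance, more predictable).
5. **Concealment.** Mix block sizes and keep the list from staff who enrol.

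The cost is a new list and three edited sentences, with no extra subjects, visits or assays. The downside is the greater predictability described above. If the list has already been drawn, item 1 no longer applies; report the block composition used and keep items 2 and 3.

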Cardiometabolic Benefits of Potatoes Mediated Along the Gut-Vessel Axis in Adults with Metabolic Syndrome

I. Objectives

The *objective of this application* is to establish evidence that incorporation of potatoes into a diet pattern based on the *Dietary Guidelines for Americans (DGA)* enhances cardiometabolic health in persons with metabolic syndrome (MetS) by improving microbiota- and host-mediated metabolic responses along the gut-vessel axis. Our central hypothesis is that the inclusion of potatoes, as part of a *DGA*-based dietary pattern, will potentiate gut barrier function and attenuate postprandial hyperglycemia (PPH)-mediated impairments in vascular endothelial function (VEF). To test this, we will complete the following objectives: 1) define changes in gut barrier function in association with improved gut microbiota composition, increased fecal short chain fatty acid (SCFA) production, and decreased serum endotoxin, 2) define changes in postprandial glycemic responses and endotoxemia, and 3) define changes in gut hormones that promote glycemic control and changes in markers of oxidative stress in relation to improvements in endothelial vascular function, all following 2-week potato consumption. Upon completing this study, we anticipate novel evidence demonstrating gut-level benefits of a potato-containing diet to lower cardiometabolic risk in MetS adults.

II. Procedures

A. Study Design

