If a participant is telephoned and is unavailable, a message will be left requesting a callback at a convenient time or that at a member of the study team will try calling again at a later time. No confidential or sensitive information will be shared with third parties or left on answering machines.

Intervention timeline. Each participant will complete a 2-arm (*DGA* + Potato; *DGA* + Bagel), randomized, cross-over study. For this study, each participant will visit the study center a total of 12 times (6 times per study arm, including 1) baseline measurements of anthropometrics, serum glucose, insulin, endotoxin, and pick-up of meals for days 1-3, 2) pick-up of meals for days 4-7 2) pick-up of meals for days 8-11 and measurement of anthropometrics, 3) pick-up of meals for days 11-14 and stool collection kit, 4) 2 h postprandial testing, and 5) return samples from 24-h urine collection. Interventions will be separated by two weeks (for women, interventions will be separated by 2, 6, 10 etc. weeks to ensure vascular testing will be performed at the same time of the menstrual cycle).

Baseline visit. On day 0 of each trial arm, participants will report in the fasted state (10-12 hours) to the study center for assessment of height, weight, waist circumference, blood pressure, serum glucose, serum insulin, and serum endotoxin. They will receive 3-4 days of *DGA* meals plus potatoes (350g/day) or bagels (1/day = 95g).

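### Does the SAP need a fixed rule for using day-0 endotoxin when it analyses the day-14 primary endpoint?

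*Combined protocol and SAP*

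**What the plan says.** Under Power Calculation, the glucose and FMD areas under the curve and "fasting endotoxin following 14-d controlled feeding have been selected as the" primary outcome variables. That section puts the need at 22 participants for a 25% lowering of endotoxin and 26 for FMD, and plans to enrol 30.

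Day-0 endotoxin is collected in each arm. Under Baseline visit, "participants will report in the fasted state (10-12 hours) to the study center" on day 0. Test trials sets the same fast for day 14. The only purpose given for the day-0 draw is in Study Design: "At baseline (day 0) of each trial, fasting glucose, insulin, and endotoxin will be measured to verify stable health status".

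The Statistical Analysis Plan describes linear mixed models with a random subject effect and "fixed effects for gender, time period, and their interactions". It names no baseline covariate, defines no change score and does not say that day 0 is left out. The covariates it mentions for the correlation analyses are unnamed. Enrollment Criteria proposes only HDL-C and blood pressure as covariates.

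Objective 1 looks for "increased fecal short chain fatty acid (SCFA) production, and decreased serum endotoxin" without saying whether the decrease is from day 0 or relative to the bagel diet.

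**The concern.** A primary endpoint has a baseline measured under the same fasting conditions, and the analysis text does not mention it. The phrase about time period could mean the crossover period. It could also be read as day 0 versus day 14, and a model with day-0 rows as outcomes gives a change-type contrast. Two analysts could then follow the same short SAP and report different results.

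Two things would be at stake. The first is precision: an unplanned change score could lose power, and ignoring a useful baseline could waste some. The second is the open choice. Taking the smallest p-value of the three analyses would raise the type I error for this endpoint from 5% to about 8.7-9.5% in simulation (n = 26 or 30).

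**Working it through.** **The plan's own figure.** The 22 for endotoxin cannot be reproduced, because no SD, CV or within-subject correlation is given. Taking it as a paired comparison with 80% power at two-sided 0.05 (both assumed), the SD of the paired difference is about 40% of the mean. The standardised effect is then 0.25/0.399 = 0.626, and power with 30 completers is 0.91 on day-14 values alone.

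**What the text supports.**
- The endpoint is defined as the value after 14 days of feeding.
- It is listed beside two day-14 areas under the curve for which no day-0 challenge is scheduled, so those have no baseline counterpart.
- The FMD power statement is a potato contrast on day 14, and the endotoxin calculation is described as similar.
- Study Design uses *period* for the crossover period, within which days 0, 7 and 14 fall.
- Nothing mentions change from baseline or baseline adjustment for endotoxin.

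The natural reading is diet versus diet on day-14 values, with day 0 as a check.

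**What adjustment would gain.** Assume unit SD and correlation r over 2 weeks, decaying as r^(lag/2 weeks). With a 2-week washout the visits fall at weeks 0, 2, 4 and 6 (B1, Y1, B2, Y2).
- var(Y1-Y2) = var(B1-B2) = 2(1-r²)
- cov(B1-B2, Y1-Y2) = r - r³ - r + r = r(1-r²)
- The correlation of the two differences is r/2, so adjustment multiplies the variance by 1 - r²/4 before the cost of estimating one more coefficient (about 2% of interval width).
- The change-score variance ratio is 2 - r, so its interval is wider by a factor √(2-r).

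Mean 95% CI width relative to day-14 only, n = 30 (simulated; the visit-noise row makes 20% of the variance independent at each visit):

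| r | 0.3 | 0.5 | 0.7 | 0.8 |
|---|---|---|---|---|
| Adjusted | +0.9% | -1.3% | -4.4% | -6.5% |
| Adjusted, 20% visit noise | +1.3% | +0.1% | -0.9% | -0.9% |
| Change score | +30% | +22% | +14% | +10% |

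If all visits are equally correlated, adjustment costs 2.0% and the change score 41%. In power terms at n = 30, 0.91 becomes at most 0.92-0.95 with adjustment and 0.65-0.86 with a change score.

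Longer gaps help adjustment. The plan allows them: "for women, interventions will be separated by 2, 6, 10 etc. weeks". A 6-week gap plus 4 weeks of feeding is 10 weeks and fits the statement that "completion of all study procedures will take ~6-12 weeks per participant"; a 10-week gap makes 14 and does not. If 8 of 30 participants had a 6-week gap (an assumption), the adjusted width would change by +0.2%, -3.1%, -8.1% and -11.2% for the same four r.

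**What adjustment would risk.** Period-2 day 0 comes after the first diet. Let the two sequences differ by c at that visit only. The adjustment slope is r/2, and the treatment effect is half the sequence contrast, so the adjusted estimate shifts by rc/4. For c = 0.5 SD this is 0.3 × 0.5/4 = 0.04 SD up to 0.8 × 0.5/4 = 0.10 SD. The unadjusted standard error is √(2(1-r²)/30), which is 0.246 SD at r = 0.3 and 0.155 SD at r = 0.8.

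At r = 0.8 the squared bias relative to the unadjusted variance is 0.010/0.024 = 0.42, while adjustment lowers the variance only to 0.84 of its value. The sum is 1.26, and estimating the slope adds the rest. The simulated mean-squared-error ratios, adjusted to unadjusted, are about 1.07, 1.10, 1.19 and 1.37 for r = 0.3, 0.5, 0.7 and 0.8, to within a few hundredths. At c = 0.25 SD the ratio is 0.97-1.03, so little or nothing is gained. If the lingering effect is a lowering by potato, the bias overstates the potato benefit.

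**The case for a change.** The strongest argument for acting is the open choice, and the precision gain is secondary to it. One clause would exclude a change score that could take power from 0.91 to 0.65, and would rule out choosing among three results. It is true that the SAP has no such clause and that writing one would be harmless. But the type I figure of 8.7-9.5% is a worst case that supposes deliberate selection of the smallest p-value, and the plan never proposes a change score. Once the endpoint is read as defined, the clause would only restate it.

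Adjustment can also look better than in the table. Let rb be the correlation of any two visits in different periods and rw that of day 0 and day 14 within a period. The variance ratios to day-14 only are then 1 - [(rw-rb)/(1-rb)]² for adjustment and 2(1-rw)/(1-rb) for a change score. With rb = 0.6 and rw = 0.8 these are 0.75 and 1.0, so the 22 becomes 18 and 22. With rb = 0.6 and rw = 0.9 they become 11 and 13. So the ranking against change scores depends on the model, and the gain from adjustment could be substantial. However, this model treats day 14 of period 1 and day 0 of period 2 as no closer than any other cross-period pair. At the planned washout they are 2 weeks apart, as close as day 0 and day 14 of one period, which makes the pattern less plausible.

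Carryover does not always count against adjustment. If the first diet's effect persists to day 14 of period 2 as well, adjustment helps. That leaves a judgement on which reasonable statisticians differ.

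**Conclusion.** No change follows. The gap is real but small: the SAP does not state what day-0 endotoxin is for in the analysis. The endpoint definition and the stated purpose of the day-0 draw lead an analyst to compare day-14 values between diets. That comparison is unbiased by design, apart from carryover into the day-14 values themselves. At most some precision is forgone.

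Requiring adjustment as the primary analysis would be a trade-off. At the planned washout the interval width changes by +2.0% to -6.5% across the equal- and decaying-correlation cases, against a mean squared error up to about 1.37 times as large if 0.5 SD of carryover sits at period-2 day 0 only. All of this rests on assumed correlations and an assumed 80% power for the 22. Endotoxin does not set the sample size (22 against 26 for FMD), so the conclusion is not sensitive to these choices. Adjustment for the within-subject day-0 difference remains available as a sensitivity analysis without altering the plan. The absence of a named treatment term in the fixed-effects list is a separate matter and does not bear on the use of day 0.

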Dietary intervention. Participants will be provided all foods for the 14-d intervention period. After the baseline visit, participants will report back to the study center on days ~3, 7, and 10 to pick up their meals for the proceeding 3-4 days. On day 7, anthropometrics (height, weight, and waist circumference) will also be measured to ensure weight maintenance. To standardize resistant starch (~12 g/d/350 g potato) and promote dietary compliance, potatoes will be prepared in several ways that minimize resistant starch degradation⁸ (e.g. Day 1 = whole baked, Day 2 = mashed, Day 3 = seasoned wedges, Day 4 = sliced, with soy milk and vegan cheese) without creating a food product that is contraindicative to a *DGA* diet (e.g. potato chips, deep-fat fried). The prepared potatoes will be refrigerated by the participants until ready for consumption, at which point they may be microwaved if desired. Participants will consume the potato daily, with a meal of their choice. Participants will be provided non-sodium seasoning (e.g. pepper blend) or may consume the potato with other foodstuffs (e.g. eggs at breakfast). Similarly, participants may choose to co-ingest the bagel with other provided foods.

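### Does the FMD sample size of 26 fail because its supporting data are an acute 0-3 h milk comparison rather than a 0-120 min AUC after 14 days of diet?

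*Combined protocol and SAP*

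**What the plan says.** Section II.B, Power Calculation, names the primary outcomes as "Plasma glucose and FMD during the 2-h postprandial period", expressed as AUC 0-120 min, together with fasting endotoxin, all after 14 days of controlled feeding.

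The only FMD data printed in support come from an earlier study: "MetS adults had improved FMD following low-fat milk ingestion compared with rice milk". The AUC over 0-3 h was 1150 ± 145 "vs 908 ± 118 , CV=56" (the CV is a percentage). The same paragraph says that postprandial hyperglycaemia was inversely related to FMD in prior work, and that the milk also blunted hyperglycaemia.

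The plan then predicts that FMD AUC "will be 25% greater in DGA+Potato during the oral glucose challenge on day 14" and concludes that "26 MetS subjects would be needed to detect a treatment effect with >80% power" at P<0.05. It enrols 30 to cover attrition and add power.

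On the exposure, section II.C, Dietary intervention, says "Participants will consume the potato daily, with a meal of their choice". On day 14 (section II.C, Test trials), "participants will report back to the laboratory in the fasted state (10-12 hours"), and "Participants will ingest a sugar solution containing 75 g glucose". The drink is the same in both arms.

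**The concern.** The supporting data differ from the trial's comparison in two ways.

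- **Window.** The earlier AUC covers three hours and the trial's covers two. No conversion is given.
- **Contrast.** In the earlier study the arms differed in what was ingested. Here both arms drink the same glucose solution after an overnight fast, so any FMD difference must carry over from the preceding diet. The predicted 25% is nevertheless almost the whole of the acute difference.

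If a carried-over diet effect were clearly smaller than the acute one, the stated power would not apply to it. FMD is one of three primary outcomes and the vascular part of the central hypothesis, so a null result could be misread as absence of benefit.

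**Working it through.** **Inputs.** From section II.B: earlier means 1150 and 908, CV 56%, predicted effect 25%, n = 26, power above 80%, P<0.05, enrolment 30. The plan does not state sidedness, the SD of the paired difference or the within-subject correlation. I assume a two-sided paired t-test with noncentral-t power, and express effects and SDs as percentages of the control mean.

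**1. Acute effect against planned effect.** (1150 − 908)/908 = 242/908 = 26.7%. The planned 25% is 25/26.7 = 0.94 of it. The sample size is stated for 25%; 26.7% is not printed in the plan.

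**2. The plan's own figure.** Take 26 as giving exactly 80% power for 25%. The required standardised paired difference is 0.572, so the SD of the difference is 25/0.572 = 43.7%. With that SD:

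| True effect | Power, 30 completers | Power, 26 completers | Completers for 80% |
|---|---|---|---|
| 25% | 86% | 80% | 26 |
| 20% | 68% | 61% | 40 |
| 15% | 44% | 39% | 69 |

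The smallest difference with 80% power is 23.1% at 30 completers and 25.0% at 26. The 25% row agrees with the plan by construction, because the SD was solved from the plan's 26. The 20% and 15% rows are illustrative effects that no part of the plan proposes.

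**3. Sensitivity to the SD.** The plan says more than 80%, so 43.7% is an upper value on this reading. If 26 gave 85% or 90% power, the SD would be 40.9% or 37.8%, and the detectable difference at 30 would be 21.6% or 20.0%.

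In the other direction, suppose the printed CV of 56% were itself the SD of the paired difference (an assumption). Then 25% needs 42 completers, power at 30 is 66%, and the detectable difference is 29.6% at 30 and 32.0% at 26.

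If instead 56% is the between-subject CV, the SD of the difference is 56 × √(2(1 − ρ)). At ρ = 0.70 this is 56 × √0.60 = 43.4%, which needs 26 completers. So 26 is consistent with the printed CV at a within-subject correlation of about 0.70, which the plan does not state. Across these readings the detectable difference at 30 runs from about 20% to 30%.

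**4. Window.** Assume the control AUC accrues evenly, so its two-hour value is 908 × 2/3 = 605, and keep the relative SD at 43.7%. The two-hour effect is then 242 × share/605, where share is the fraction of the difference arising in the first two hours.

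| Share in first 2 h | Effect on 0-2 h AUC | Completers for 80% |
|---|---|---|
| 40% | 16% | 61 |
| 50% | 20% | 40 |
| 67% | 27% | 24 |
| 80% | 32% | 17 |

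Proportional accrual (67%) gives 24, slightly fewer than 26. The shares are assumed, and the result has no fixed direction.

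**The case for a change.** The strongest case for a change is that the plan offers no FMD data for a repeated-feeding contrast and no 0-120 min figures, and that power falls quickly below 25%. At a true 15% effect, non-significance is more likely than not even with 30 completers. A recalculation from the team's own earlier time-course data would cost little. Using the printed CV as the paired SD would make the picture worse, at 66% power for 25%.

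The facts in this stand. The basis for 25% on this endpoint is thin, and a reader cannot recover 26 without supplying a correlation.

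The inference to a missed power target does not stand. The 66% depends on reading 56% as the SD of a within-person difference, which the plan does not say; in a crossover, a between-subject CV with a correlation near 0.70 gives 26. The illustrative effects below 25% have no source in the documents, and at 20% significance is still the likelier result (68% at 30 completers, 61% at 26). Nor is the carry-over wholly without rationale: section II.B links hyperglycaemia to FMD, and section I states the hypothesis as diet reducing hyperglycaemia-mediated vascular impairment. That gives a mechanism, though not a size.

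**Conclusion.** No change to the plan follows. The supporting data come from a different window and a different kind of contrast, and the plan does not bridge the gap. But it sizes the trial on an explicit prediction of 25%. With the SD implied by its own 26, that prediction has 80% power at 26 completers and 86% at 30. The window argument cuts both ways, from 17 to 61 completers depending on an assumed share.

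What is left is a view that 25% may be optimistic for a two-week diet effect. That is a design judgement, and the documents contain nothing with which to replace the figure. Enrolling more would mean two fully fed 14-day periods and 12 visits for each extra participant, on the strength of an effect size chosen by the critic. A reworded power statement or a note on confidence intervals would alter no result.

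This conclusion assumes a two-sided paired test and rests on the back-solved SD. It does not establish that 25% is realistic, only that the documents do not show the trial to be underpowered for it. Anyone interpreting a null FMD result should bear in mind that the difference detectable with 80% power at 30 completers is about 20% to 30%, depending on the SD.
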